Official Title: Mitochondrial function in circulating cells and muscle tissue

NCT02700698

Document Date: 03/21/2019

Study Title: **Mitochondrial function in circulating cells and muscle tissue**

Principal Investigator: [name].
Office: [contact]
[contact] (cell)

Co-Investigators: [name].
[name].
[name].
[name].

Study Physician: [name].

Study Location: Arkansas Children's Nutrition Center (ACNC),
Arkansas Children's Hospital Research Institute,
[name]
[name]
and
University of Arkansas for Medical Sciences
Reynolds Institute on Aging, Little Rock, AR 72205

Funding: Arkansas Children's Nutrition Center (ACNC)
United States Department of Agriculture (USDA)

Background

Data from human and animal models strongly suggests that reduced tissue mitochondrial function can be an early marker for detection of dysfunctional metabolism [1]. It is unclear if tissue mitochondrial dysfunction can be detected using less invasive methodology. In this project, we plan to study mitochondrial bioenergetics in circulating cells and paired muscle biopsies in two metabolic disparate groups of women: healthy lean vs. overweight/obese and/or insulin resistant women of similar age.

Mitochondria in circulating blood cells sense oxidative stress during capillary passage and react by producing reactive oxygen species (ROS) [2]. Bioenergetic profiling of readily available circulating cells has recently been proposed to reflect systemic mitochondrial health/fitness, physical function and inflammation [3, 4]. Thus, the mitochondria function in circulating cells may potentially inform on the overall metabolic health in an individual. The “bioenergetic health index” (BHI) in peripheral blood mononuclear cells (PBMC) and/or platelets has therefore been described as a potential new biomarker for assessing patient health [3, 5, 6].

Studies to date have, however, not compared results of mitochondrial function in circulating cells and in muscle tissue in the same persons. Instead, a relation has been shown indirectly by an association between the bioenergetics of PBMC and physical function and inflammation in overweight/obese older adults [4]. Thus, there is a need for establishing this relation by comparing bioenergetics in circulating cells and in muscle tissue from the same individual, and in individuals with contrasting metabolism.

By studying healthy lean and overweight/obese and/or insulin-resistance women of the same age, we expect to discover differences in muscle mitochondrial function in the two groups, with compromised function in the overweight/obese and/or insulin resistant group. Obesity is associated with metabolic impairments in peripheral tissues and dysfunctional adipose tissue unable to buffer the flux of dietary lipids, leading to ectopic lipid deposition and lipotoxicity in other organs. Lipid accumulation in skeletal muscle is associated with insulin resistance and overall cellular dysfunction, with mitochondrial dysfunction as one of the underlying mechanisms [7]. We hypothesize that PMBC mitochondrial function in the overweight/obese and/or insulin resistant group is compromised compared to the healthy lean group. Finally, we hypothesize that there will be a relation between PBMC and muscle mitochondria function across the two groups.

The main goal of this project is to determine whether mitochondrial function in circulating cells is related to that measured in the muscle fibers of the same subjects, and if differences can be observed when comparing metabolic dissimilar groups. Considering the difficulty of obtaining muscle biopsies from various populations, especially pediatric populations, it would be a major step if a blood sample can inform about overall/tissue mitochondrial health.

Study Design:

Twenty (20) healthy lean, and 20 overweight or obese and/or insulin resistant women of similar age will be recruited, with the goal of 15 women/group completing the study.

Inclusion criteria:

- Women.
- 25-35 years of age.
- Either healthy lean ($BMI < 25$), or overweight ($25 \leq BMI < 30$) or obese ($BMI \geq 30$) and/or insulin resistant.

Exclusion criteria:

- Pre-existing medical conditions (e.g., chronic renal failure, bleeding disorders, heart disease, self-reported hepatitis or HIV, thyroid disorders) that can affect study outcomes, as determined by the PI and/or designee.
- Self-reported possibility of current pregnancy.
- Regular smoking.
- Alcohol or drug abuse.

Enrollment/Recruitment: Various advertisements will be distributed by direct mail or to various locations, including but not limited to healthcare offices, weight loss clinics, health fairs, schools/universities, recreational centers, websites (ACH, ACRI, ACNC, UAMS, and others as applicable) and churches. Also, print or digital ads may appear in newspapers, magazines, social media and circulars. Recorded phone messages that play when the phone is answered and the person is on hold, BoomText messages, screensavers, and radio/television advertisements may be used. We will also work with physicians, who have patients that may qualify as potential volunteers. They will in that case administer a flyer to the potential subject and ask them to contact us if they are interested in participation.

A standardized screening script will be used to determine whether potential participants qualify for the study. Potential participants will be asked if their information can be saved for consideration in future studies and their response will be documented. We will protect all personal information obtained during recruitment, enrollment, and testing processes, and maintain this in a closed office.

Informed Consent Process: During the informed consent process, the PI, co-Is, or a research staff member will review all study procedures and the informed consent documents with the potential participant. If eligible and interested in enrollment, informed consent from the participant will be obtained and documented. The participant will be given ample time to review the consent form, ask questions and receive clarification prior to signing any documents.

Study Procedures: The participants that qualify and sign consent for this study will come only once to the Reynolds Institute on Aging at UAMS or to the ACNC where the visit will take place, depending on room and physician's availability.

The visit will take 2-3 hours and the participant will arrive after an overnight fast. At the visit, vitals anthropometrics will be recorded, body composition may be measured, a blood sample will be collected and a muscle biopsy sampled.

- Vitals and Anthropometric measures: The subject's blood pressure, pulse, temperature, body mass, height, and waist and hip circumferences will be obtained using standardized techniques.
- Physical activity questionnaire: A questionnaire (attached) will be administered to record physical activity. This will enable us to control for levels of physical activity between participants.
- Dual-Energy X-ray Absorptiometry (DXA): Body composition may be measured using a DXA device (Hologic Inc, MA, USA). This technology involves very small amounts of radiation. The subject will be asked to lie down without moving during the entire length of scanning (about 5

min). The scanning process will be aborted at the request of the participant or if any movement occurs. This procedure may be repeated if the first one is invalid or is aborted.

- Blood collection: Blood will be collected by a trained phlebotomist. In total, ~50 ml (~3.5 tablespoons) will be drawn for isolation of PBMC and platelets, and for analyses of insulin, glucose, lipid levels, and other analytes such as metabolites or hormones.
- Muscle biopsy: After the blood draw, a muscle tissue biopsy will be taken from m. vastus lateralis, about 4-6 inches above the knee by [name]. Before any incisions are made, the skin will be cleansed with an antiseptic scrub solution and allowed to dry, and the skin and tissue below injected with lidocaine. A small incision about the size of this dash “—“ will then be made, through which a needle about the size of the letter “O” is gently pushed into the muscle. A piece of the muscle is then removed with the needle. The skin will thereafter be closed with dermabond glue, and a light dressing applied. The biopsy site will be iced, a biopsy procedure note recorded, and the subject will be given thorough oral and written instructions about how to care for the biopsy site (please see attachments).

The biopsy will immediately be placed in a BIOPS buffer and analyzed for mitochondrial function within a few hours after sampling. We have established the protocol for determination of mitochondrial function in permeabilized muscle tissue using high resolution respirometry (Oxygraph O2k, Orophorus Instruments, Innsbruck, Austria) [8]. Similarly, the co-investigator [name], MD, at ACHRI has established protocols on determination of mitochondrial function in cells, using the Seahorse Extracellular Flux (XF) 96 Analyzer (Seahorse Bioscience, North Billerica, MA, USA).

Sample Storage: Blood and muscle samples will be kept at -80°C once the initial processing and analyses have taken place. Samples will be stored in appropriate freezers in the PI's laboratory. These are monitored continuously for proper temperature and working condition. Samples will be destroyed only after all data has been analyzed and reported. All blood and muscle samples will be using a unique study acronym. None of a subject's personal identifiers will be present on any biological sample.

Statistical and Power Analyses: Forty women between 25-35 years old (20 healthy lean and 20 insulin-resistant and/or overweight or obese) will be recruited to participate in this study. Assuming a moderate dropout rate of 25%, we anticipate the final sample size to be 30 (15 healthy lean and 15 insulin resistant

and/or overweight or obese). A two-sample t-test will be used to assess differences between means of the two groups for either the blood or the muscle measurements. In addition, correlation and concordance analyses will be performed between the blood and the muscle results across the two groups to assess their correlation and agreement. Outcome variables will be checked to verify that the distributional assumptions (normality) for the t-test are met. When substantial deviation from assumptions is encountered, and if a suitable data transformation is not found, groups will be compared using the nonparametric Wilcoxon/Mann-Whitney rank-sum test.

Power analysis: Using the 2-sample t-test with equal variance, a sample size of 30 (with 15 subjects per group) achieves 80% power to detect a standardized difference of 1.06 units between the two group means versus the null hypothesis of equal means at a 5% α -level. Alternatively, without any dropout, a sample size of 40 (with 20 subjects per group) achieves 80% power at 5% α . Although the effect sizes are estimated to be moderate to large, it will provide valuable information regarding whether a larger study is warranted, and will form a basis for statistical approaches to other planned follow-up studies.

Data Safety Monitoring Plan

All investigators, co-investigators and study staff will complete and maintain appropriate CITI training. All data and communications will be recorded in standardized case report forms to ensure a paper copy trail. Source documents and CRFs will be stored in a secure area of the PI's laboratory. Access will be limited to study personnel. Documents will be archived according to UAMS/ACH/ACNC policies regarding destruction of research records. At no time shall Protected Health Information be released to non-study personnel.

Research data will be entered into a clinical database. This database will be housed on a shared drive backed up nightly off-site Monday – Friday. Access to our server is password protected, as is access to the study database(s). Access will be limited to study personnel.

Discomforts and Risks

The risks associated with the study procedures are as follow:

- **DXA:** The DXA instrument uses radiation to measure body composition. The radiation exposure is small (< 0.1 mrem) corresponding to approximately 2 days' worth of the naturally occurring radiation a person is exposed to while living in the Little Rock Area.
- **Blood Sampling:** The total amount of blood drawn for this study will be approximately 50 ml (~3.5 tablespoons), which is only 1/5 of what is generally given during blood donations. Aseptic technique will be followed which will minimize the risks of infection. However, the risks related to blood draw include pain and bruising.
- **Muscle biopsy:** The muscle biopsy procedure is performed under local anesthesia (1% lidocaine with a small amount of bicarbonate) for normal pain management, and possible formation of a bruise from local bleeding. Bleeding from the muscle biopsy site is highly unlikely since no major arteries or veins are located in the region. A possible complication of this procedure is infection due to lack of sterility during the procedure. General precautions that will be taken include strict sterility during muscle biopsies. At the end of the study, the small incision at the biopsy sites will be dressed with an antibiotic ointment to minimize risk of infection. Further, pressure bandage and ice will be applied.

Safety Reporting

Definitions

- Related: For this policy, an event is “related” if it was caused by participation in the research activity or there is a reasonable possibility that the event may have been caused by the procedures involved in the research.
- Risk: The probability of harm or injury (physical, psychological, social or economic) occurring as a result of participation in a research study.
- Unanticipated: A problem is “unanticipated” when it was unforeseeable at the time it occurred.
- Unanticipated Problem Involving Risks to Subjects or Others (UPIRTSO): Any problem, event or new information that is:
 - 1) Unanticipated or unexpected;
 - 2) Related to the research; and

- 3) Involves new or increased risks to subjects or others.
- E. Unexpected: An event is “unexpected” when its specificity, nature, severity or incidences are not accurately captured in the approved consent form. Examples include a lower rate of response or a side effect that is more severe than initially expected.

(Serious) Adverse Events handling

Any clinical study event that is judged to be an (S)AE, either reported spontaneously by the subject or observed by the investigator or her/his staff, is recorded on the (S)AE form during the course of the study. The investigator must ensure that this information, including onset, duration and nature of event, severity, and action taken, is captured.

The severity of any (S) AE is scored as follows:

- Mild: transient or mild discomfort; no medical intervention/therapy required.
- Moderate: mild to moderate limitation in activity; some assistance may be needed; and/or minimal medical intervention/therapy required.
- Severe: marked limitation in activity; some assistance usually required; and/or significant medical intervention/therapy/hospitalisation required.

We do not foresee any adverse events associated with this protocol. In addition, testing can be aborted at any time at the participant's request. All procedures are minimally to moderate invasive. However, any adverse effects or unanticipated problems will be reported to the study PI, the IRB, and the study sponsor in accordance with UAMS IRB Policy 10.2 Information that Must Be Reported to the IRB and IRB Actions.

Risks/Benefits

Participants will not directly benefit from this study. Future population may benefit from this research. Expected risks associated with this protocol are described in detail above. All experimental procedures will be performed by appropriately trained and credentialed personnel.. Potential risks from participation in this research protocol include problems associated with blood drawing and muscle biopsies.

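### Does the lack of an insulin-resistance criterion leave the group label open in the t-tests?

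*Combined protocol and SAP*

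**What the plan says.** The Background describes a study "in two metabolic disparate groups of women: healthy lean vs. overweight/obese and/or insulin resistant women of similar age". The inclusion criteria under Study Design give the lean category as "Either healthy lean ($BMI < 25$), or overweight", and continue with the overweight and obese BMI limits and insulin resistance joined by and/or. The Statistical and Power Analyses section repeats the and/or definition for the 20 women in the comparison group. Insulin resistance alone is therefore enough for that group, but no section gives an index, a cut-off or a diagnostic rule for it.

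On timing, Enrollment/Recruitment states: "A standardized screening script will be used to determine whether potential participants qualify for the study". The script's content is not in the documents. Study Procedures adds: "The participants that qualify and sign consent for this study will come only once", and "the participant will arrive after an overnight fast". Blood is drawn at that visit "for analyses of insulin, glucose, lipid levels, and other analytes such as metabolites or hormones", and the muscle biopsy follows the draw. The protocol does not say when a woman's group for analysis is fixed.

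The label is used in the two-sample t-tests (rank-sum test as fallback) on the blood and the muscle measurements. Correlation and concordance between blood and muscle are computed across both groups together.

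**The concern.** One route into the comparison group has no measurable definition, and the only data described that could settle it arrive after a woman has qualified. The word healthy, or a question in the screening script, could keep known cases out of the lean group but could not detect undiagnosed ones. A woman recruited as lean could then prove insulin resistant on the study's own fasting sample. Muscle respirometry is run within hours of the biopsy, so her outcome might exist before her label is settled, and no blinding of group assignment is described.

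The group comparison is at stake. The protocol hypothesises that PBMC "mitochondrial function in the overweight/obese and/or insulin resistant group is compromised compared to the healthy lean group", and the second half of its main goal asks "if differences can be observed when comparing metabolic dissimilar groups". If the label could be set after the results are seen, the 5% error rate of those t-tests would no longer hold. If such women stayed in the lean group, the groups would also not match the stated definition.

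**Working it through.** **The plan's own figure.** Inputs from the Power analysis paragraph: 15 women per group, standardized difference 1.06, 5% level, equal-variance two-sample t-test (two-sided assumed, since the side is not stated). The noncentrality is 1.06 × √(15/2) = 2.90 on 28 degrees of freedom, which gives power 80.0%. The stated 80% reproduces. Allowing for dropout, 30/(1 − 0.25) = 40, which matches recruitment.

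**Does the text place the woman?** The Background, Study Design and the statistics section all use the same and/or definition. A woman with BMI below 25 who meets insulin resistance satisfies it, so she belongs to the comparison group. No section provides for excluding her. What is unwritten is the threshold, and a statement that the visit result sets the label.

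**Type I error under a fixed rule.** Simulated trials with no true difference and 1, 2 or 3 such women among the lean recruits: always keep them as lean, always move them, or always leave them out. Each rule alone rejects in 5.0% of trials, with 15 or 20 per group.

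**Type I error if labels are chosen after results.** Take the smallest p-value over the permitted choices, with no true difference (200,000 or more simulated trials per case):

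| Such women | 15/group, one choice for all | 15/group, woman by woman | 20/group, one choice for all | 20/group, woman by woman |
|---|---|---|---|---|
| 1 | 6.7% | 6.7% | 6.5% | 6.5% |
| 2 | 7.4% | 8.9% | 7.1% | 8.2% |
| 3 | 7.9% | 11.8% | 7.5% | 10.6% |

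Repeat runs differ by about 0.1 to 0.2 of a point.

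**How many such women?** The documents give no share, so 5% and 10% are assumptions. The chance of at least one among 15 is 1 − 0.95^15 = 54%, or 1 − 0.90^15 = 79%. The binomial probabilities of 0, 1, 2 and 3 or more are 0.463, 0.366, 0.135 and 0.036 at 5%, and 0.206, 0.343, 0.267 and 0.184 at 10%. Weighting the 15-per-group error rates for one choice for all, with 3 or more counted as 3:

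- 5% share: 0.463 × 5 + 0.366 × 6.7 + 0.135 × 7.4 + 0.036 × 7.9 = 6.05%.
- 10% share: 0.206 × 5 + 0.343 × 6.7 + 0.267 × 7.4 + 0.184 × 7.9 = 6.8%.

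These averages assume the most favourable choice is taken every time. With no such women, the rate is 5%.

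**Power.** At 15 per group and a difference of 1.06, suppose 1, 2 or 3 such women fully resemble the comparison group. Keeping them as lean then gives 73%, 66% and 58%. If instead they do not differ from lean women at all, moving them gives 73%, 66% and 59%. The loss simply changes sides with an assumption that the documents do not settle, so power favours no particular rule.

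**The case for a change.** The strongest case for a change is that the label is the only explanatory variable in the t-tests, and that the Background itself links insulin resistance to mitochondrial dysfunction in muscle. The ambiguous women are thus the ones whose label could matter most. Choosing woman by woman more than doubles the error rate with three such women, and writing down a criterion would need no new samples or visits.

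Part of this stands. The threshold is missing, and the text does not say that the visit result governs. A careful analyst would record both before opening the mitochondrial data.

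The rest does not carry. It is an inference that such a woman would be analysed as lean, because the timing of the label is not given and labelling from the visit sample fits the text. The three-way choice of keep, move or leave out is wider than the protocol allows, since its definition points to one answer. The inflated error rates need post hoc selection, of which the plan gives no sign. An amendment would also have to supply a cut-off for which the documents offer no basis, and it would bring no predictable gain in power.

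**Conclusion.** The concern does not call for a change. The omission is real but is one of detail: a term used in the group definition lacks a written threshold. The definition itself assigns the woman in question, the fasting insulin and glucose needed to apply it are already collected, and any criterion fixed without reference to the mitochondrial results leaves the t-tests valid at 5%.

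The error rates of 6.7% to 7.9% (one choice for all) or up to about 12% (three women, chosen one by one) at 15 per group rest on three conditions together: such women are present, there is no true difference, and the label is picked for its result. The documents establish none of these. The blood-muscle relation, named first in the main goal, is assessed by pooled correlation and concordance, which use no label and are unaffected as long as no woman is dropped. The Power analysis paragraph also presents the study as a guide to whether a larger one is warranted, which limits the weight of any single t-test. Analysts can be expected to fill this gap sensibly when they prepare the data.

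### The blood-muscle correlation is planned only pooled across the two groups, so it cannot separate a relation between women from a difference between groups; report a group-adjusted estimate beside it

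*Combined protocol and SAP*

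**What the plan says.** The Background section states the main goal: to "determine whether mitochondrial function in circulating cells is related to that measured in the muscle fibers of the same subjects", and to see whether metabolically dissimilar groups differ. It gives three expectations. For muscle, "we expect to discover differences in muscle mitochondrial function in the two groups", with function compromised in the overweight, obese or insulin-resistant group. For PBMC, the hypothesis is that "mitochondrial function in the overweight/obese and/or insulin resistant group is compromised compared to the healthy lean group". The third expectation concerns the link between the two tissues: "we hypothesize that there will be a relation between PBMC and muscle mitochondria function across the two groups".

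The Statistical and Power Analyses section plans t-tests between groups and then says that "correlation and concordance analyses will be performed between the blood and the muscle results across the two groups to assess their correlation and agreement". It plans no within-group or group-adjusted correlation. The power statement covers the t-test only.

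Under Study Procedures, the muscle assay is described as "determination of mitochondrial function in permeabilized muscle tissue using high resolution respirometry" and the blood-cell assay as "determination of mitochondrial function in cells, using the Seahorse Extracellular Flux (XF) 96 Analyzer". The supplied text gives no scale common to the two, and it does not name the concordance coefficient.

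**The concern.** The two groups are recruited to differ metabolically, and the protocol expects both tissues to be worse in the same group. When two measures each differ between groups in the same direction, they correlate in the pooled sample even if, among women of the same group, one says nothing about the other. The pooled coefficient mixes these two sources and nothing else in the plan separates them.

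This bears on the main goal. A significant pooled correlation could be read as evidence that a blood sample reflects a woman's own muscle function, when it may show only that both tissues differ between lean women and the comparison group. The Future plans section looks ahead to blood measurements possibly replacing biopsies, so that reading is a likely one.

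The agreement wording raises a smaller question. Agreement in the absolute sense needs both measurements on one scale, and permeabilized muscle and isolated cells are measured on different instruments with no stated conversion.

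**Working it through.** **The plan's own figure.** A two-sample t-test with 15 per group, standardized difference 1.06 and two-sided 5% level has noncentral-t power 0.8001. The stated 80% reproduces. The document gives no power or precision for the correlation.

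**Inputs.** From the Statistical and Power Analyses section: 15 per group (30 women) after dropout or 20 per group (40) without, and the shift of 1.06 SD. Assumed: shifts of 0.5 and 1.5 SD as a range, the within-group correlation rw, within-group SD of 1 in both measures, and bivariate normality.

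**Pooled correlation.** With equal groups, muscle shift dm and blood shift db:

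pooled r = (rw + dm·db/4) / √[(1 + dm²/4)(1 + db²/4)]

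With rw = 0 and equal shifts d, this is (d²/4)/(1 + d²/4). Rejection rates come from 100,000 simulated studies per case, two-sided 5%, with N−2 df for the pooled test and N−3 df for the partial correlation given group.

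| Shift in both (SD) | Pooled r when rw = 0 | Pooled test significant, n = 30 | n = 40 | Group-adjusted test |
|---|---|---|---|---|
| 0.5 | 0.0625/1.0625 = 0.06 | 6% | 6% | 5% |
| 1.06 | 0.2809/1.2809 = 0.22 | 22% | 28% | 5% |
| 1.5 | 0.5625/1.5625 = 0.36 | 54% | 68% | 5% |

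A pooled r of 0.36 is therefore what one would see with no within-group relation and a shift of 1.5 SD, or with a within-group correlation of 0.36 and no shift. The pooled analysis cannot tell these apart.

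**Both tissues must shift.** With rw = 0, muscle shifted 1.06 and blood 0.5, pooled r = 0.1325/√(1.2809 × 1.0625) = 0.11 and the pooled test is significant in 9% of studies at n = 30. With blood shifted 0, pooled r is 0 and the rate is 5%. Pooling can also understate: with rw = 0.7, muscle shifted 1.06 and blood 0, pooled r = 0.7/√1.2809 = 0.62.

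**What adjustment costs.** With rw = 0.5 and both shifted 1.06, pooled r = (0.5 + 0.2809)/1.2809 = 0.61. Power at n = 30 is 97% pooled and 81% adjusted; at n = 40 it is 99% and 92%. With rw = 0.3 at n = 30 it is 75% and 36%.

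**Precision at n = 30.** By Fisher's z, for an observed r of 0.5 (z = 0.549), the standard error is 1/√27 pooled and 1/√26 adjusted. The 95% intervals are 0.17 to 0.73 and 0.16 to 0.73.

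**Agreement, on an absolute reading only.** Lin's coefficient is 2·r·s1·s2 / [s1² + s2² + (m1 − m2)²]. Take r = 1, means 1 and k, and the same CV in both measures (assumed 20% to 30%).
- k = 1.1: 0.89 to 0.95.
- k = 2: 2(0.2)(0.4)/(0.04 + 0.16 + 1) = 0.13, to 2(0.3)(0.6)/(0.09 + 0.36 + 1) = 0.25.
- k = 10: 0.01 to 0.02.

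The loss runs from small to near total at perfect correlation, and the document gives no units or means to say which applies.

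**The case against.** The strongest reply is that pooling is the declared design. The Background asks for the relation in people with contrasting metabolism, and the hypothesis is worded across the two groups. Co-variation carried by group is then part of the target. This stands, and it is why the pooled correlation should stay.

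It follows that a reader who takes the 22% or 54% as an inflated type I error would be wrong. In those cases the population pooled correlation really is 0.22 or 0.36, so the rates are power for a true pooled hypothesis. They show only that the pooled test does not answer the narrower question of whether blood tracks muscle among comparable women. The effect is also negligible at a shift of 0.5 SD and absent if only one tissue shifts.

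On agreement, a reader might infer that the concordance analysis is invalid as planned. The document does not support that, because it does not say which coefficient will be used. Rank concordance is unit-free, and for two measures Kendall's W is just (1 + Spearman's rho)/2. Lin's coefficient on values standardized over the pooled sample equals Pearson's r. The problem arises only if absolute agreement is computed on measured values.

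Blood is collected so that it "will be drawn for isolation of PBMC and platelets", which might suggest that the cell type to pair with muscle is left open. It is not open for the stated hypothesis, which names PBMC.

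Nor do the documents make the replacement of biopsies an endpoint. It appears only under Future plans, so the absence of a prediction-error analysis is not a defect of this plan.

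**Conclusion.** The concern holds in a limited form. The pooled correlation matches the stated hypothesis and is not wrong, but on its own it cannot separate a relation between women from a difference between groups, and the main goal needs that separation. If both tissues shift by the plan's detectable 1.06 SD, group difference alone gives a pooled r of 0.22, with a significant result in 22% of studies at n = 30 and 28% at n = 40. The size depends on the true shifts, which the document does not give, and on normality with equal within-group SDs.

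The agreement point is secondary and conditional. It touches neither the t-tests, their stated power, nor the correlation. Every size given for it rests on assumed CVs and mean ratios.

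**What to change.** In Statistical and Power Analyses:

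1. Keep the pooled PBMC-muscle correlation and report it with its 95% confidence interval.
2. Report beside it a group-adjusted correlation (the partial correlation given group, on N−3 df) with its 95% confidence interval.
3. State that any claim that blood reflects muscle function in individual women will rest on the adjusted estimate.
4. State that absolute-agreement statistics will not be applied to the measured values of the two assays, or delete the agreement aim.

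The cost is wording and a little more analysis on the same paired data, with no added samples or visits. The adjusted test has less power (81% against 97% in the example above) and its interval will be wide at about 30 women. The plan should say so.
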